### Inclusion Criteria

Children aged between 1-14 years who are scheduled for elective Abdominal Laparoscopy will be eligible for this study.

### Exclusion Criteria

Exclusion criteria will be parental or patient refusal, Body Mass Index (BMI) > 40, history of prematurity (birth at post-conceptual age < 37 weeks) or history of congenital lung disorder, clinically recognized airway disease, obstructive or restrictive lung disease, pulmonary hypertension, congenital or acquired heart disease, history of intrathoracic instrumentation, history of severe brain injury and intracranial hypertension.

In addition, all patients who, from the induction of anesthesia until the deflation of pneumoperitoneum, will present any cardiovascular or respiratory major complication (i.e. massive blood loss, arrhythmia, laryngospasm, bronchospasm) will be excluded from the study. In addition, patients will be excluded in case laparoscopy will be converted to open operation due to surgical reasons.

## Removal of Patients from Therapy

Hemodynamic instability during the RM will be the main cause for removing patients from therapy, defined as persistent Hypotension (SBP <70 mm Hg in those 1–4 years, <80 mm Hg in those 5–12 years, and <90mm Hg in those >12 years). Hypoxemia (oxygen saturation <92%), bradycardia (heart rate <80 bpm in those <2 years, <60 bpm in those > 2 years) or arrhythmias will also impose the removal of RM and application of therapeutic measurements in case the symptoms insist.

## Randomization

In order to perform Randomization, the investigators will use web-software-generated blocks (available at: <http://www.randomization.com/>). Patients will be randomized to one of the two Ventilation Management Groups (RM or Control group) with 15 patients per group. Each patient assigned to participate in the study will have a sequentially numbered (from 1 to 30) sealed envelope containing Randomization Code (A or B). The Principal Investigator will be the only person who will be aware of the correspondence between Codes and study Groups. The envelopes will be concealed until deflation of pneumoperitoneum, just prior to application of RM (or not). All operations will be performed by the same team of surgeons and by the same anesthesiologists (PI and Second Investigator). In Appendix 1, there is an example of performed permuted blocks randomization with 30 patients, created by this web-software.

## Interventions & Treatments

### Anesthetic Management (prior to manipulation)

Patients of each group will have the same standardized anesthetic management.

#### Preoperative assessment

Preoperative assessment will be conducted to all eligible patients by the Principal Investigator (PI) according to local routine practice, few days or the day before the operation. During the preoperative evaluation, PI will obtain written informed consent (see below: Ethics).

#### Premedication

Patients will be premedicated 30-60 minutes before the procedure with midazolam 0,5 mg/kg po (maximum dose: 15mg).

#### Monitoring and Induction

ASA Standard noninvasive monitors will be applied before the induction of anesthesia. Induction will take place with inhalational technique with sevoflurane. When patients will reach stage 3 of anesthesia, an intravenous catheter will be inserted. Tracheal intubation, with a cuffed Endotracheal Tube (ETT) appropriate for each patient's size, will be performed after the iv administration of fentanyl 1 mcg/kg, lidocaine 1 mg/kg, rocuronium 0,6 mg/kg and adequate low doses of propofol, if necessary. The ETT cuff pressure will be measured with a Portex low pressure scale manometer and will be maintained at 20-25 cm H2O. After the

induction, an arterial catheter will be placed in the radial artery for invasive blood pressure monitoring and blood gas measurements.

#### Maintenance of anesthesia

Maintenance of anesthesia will be performed using sevoflurane (MAC: 1,2-1,4) and a mixture of oxygen and air (FiO2 0.4). Fentanyl and/or remifentanyl will be used for intraoperative analgesia as appropriate.

Ringer's Lactate solution will be used for routine intraoperative fluid management.

Maintenance doses of rocuronium will be guided by Monitoring of Neuromuscular Function of the Ulnar nerve with a Peripheral Nerve Stimulator, to maintain Post-Tetanic Count 1-2.

Subsequent care will be at the discretion of the anesthetic team and will not be part of the study.

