### Brief description

This will be an Interventional, Prevention, Parallel Assignment, Double-blind (patient, care-giver, outcomes Assessor), Randomized, Safety / Efficacy Study. We will use two parallel groups of children aged 1-14 years who are scheduled for elective Abdominal Laparoscopy

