## Abstract

### Introduction

Pneumoperitoneum and increase in Intra-abdominal Pressure in Children Laparoscopy reduces diaphragmatic excursion and shifts the diaphragm cranially, resulting in the reduction in Lung Compliance and Functional Residual Capacity and Ventilation – Perfusion (V/Q) mismatch leading, finally, to atelectasis, hypoxemia and hypercapnia. In a prospective randomized double-blind clinical trial, the investigators will test the hypothesis that alveolar Recruitment Maneuver (RM) during Laparoscopy in children aged 1-14 years improves Lung Compliance. The primary endpoint of the study will be the improvement in dynamic lung compliance ( $Com_{dyn}$ ) ( $dv/dp$ ) while the improvement in gas exchange (increase in  $PO_2$ ,  $PO_2/FiO_2$ , and decrease in  $PCO_2$ ) will be the secondary endpoint of the study.

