### Reversal of the residual blockade, Extubation and Post-Anesthesia Care

At the end of the procedure, residual neuromuscular blockade will be reversed with adequate doses of suggamadex. Tracheal extubation will be performed and the patient will be transported to the Post-Anesthesia Care Unit (PACU) according to the local practice. Patients will be discharged according to standard PACU discharge criteria.

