## Efficacy and Safety Issues

The efficacy of the RM to improve  $Com_{dyn}$  and gas exchange is the main issue of this study. The investigators regard that  $Com_{dyn}$  will be statistically significantly improved in the RM group compared to Control group. In this study, we consider clinically significant a 20% increase in the weight corrected mean  $Com_{dyn}$  in the RM group.

This improvement in lung compliance maybe would not be clinically significant, as our study population consists of healthy children (children with ASA I-II classification). Nevertheless, the possibility of underlying comorbidities should always be taken into account and anesthesia in addition to these comorbidities could negatively influence cardiovascular and pulmonary function, and thus patients' outcome. This is the reason that ventilation strategy adopted in this study has a protective-lung ventilation strategy orientation, with lower  $V_t$  and higher PEEP than usual in clinical practice the past years.

The investigators regard that there would be statistical significant difference within RM group, as well.  $Com_{dyn}$  is expected to be significantly improved in post-RM measurements in comparison to baseline  $Com_{dyn}$ , for the patients of RM group. A 20% increase in  $Com_{dyn}$  would be clinically significant too.

Secondarily, the investigators regard that RM will improve post-RM intra- and post-operative  $PO_2$  and ratio  $PO_2/FiO_2$ . For the population of this study (children ASA I-II), this improvement may also not have a clinically significant impact.

Although recruitment procedures are generally well tolerated with few adverse effects, there are several potential complications that could occur.

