## Blinding Procedure

This will be a Double-blind clinical study. Patients will not be aware of ventilation strategy during the operation. The only un-blind person will be the Principal Investigator (PI). After the RM (or not), at T4 point time (see below), a Second Investigator (SI) will come into the operating room and will record measurements from monitor. The same person will also perform blood gas analyses on the specified time points and postoperative records in PACU. The measurements will be recorded in special files for each separate patient with patient id number and then will be entered in a SPSS data file (SPSS version 22) and will be analyzed. Analysis will be performed by the two investigators separately (the PI will be un-blind) and results should be matched.

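### Later anaesthetic care is declared outside the study although T6 gas exchange is an efficacy outcome; emergence co-interventions go unrecorded and the care-giver is not masked as claimed

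*Protocol*

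**What the plan says.** The last sentence under Maintenance of anesthesia reads "Subsequent care will be at the discretion of the anesthetic team and will not be part of the study". Three other sections do govern later care:

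- Ventilation Strategy (post-manipulation) returns the RM group to the standardized ventilation and keeps controls on the same strategy throughout surgery.
- Reversal of the residual blockade, Extubation and Post-Anesthesia Care names the reversal agent, then leaves the rest open: "Tracheal extubation will be performed and the patient will be transported to the Post-Anesthesia Care Unit (PACU) according to the local practice".
- Follow up measurements says that routine oxygen is given for 30 minutes postoperatively and noted.

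On who gives the care, Randomization says all operations are done "by the same anesthesiologists (PI and Second Investigator"), and Blinding Procedure says "The only un-blind person will be the Principal Investigator (PI"). Brief description nevertheless labels the trial "Double-blind (patient, care-giver, outcomes Assessor").

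On outcomes, the Abstract says improved gas exchange "will be the secondary endpoint of the study". Efficacy and Safety Issues adds that "the investigators regard that RM will improve post-RM intra- and post-operative" PO2 and PO2/FiO2. The last blood gas is at T6, 30 minutes after PACU admission (Time points of measurements, Appendix 6).

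**The concern.** Randomization protects the T6 comparison only if care between the manoeuvre and T6 does not depend on the arm. Reversal, emergence and extubation all fall in that interval, and what happens there can change oxygenation. The manoeuvre itself is delivered in manual mode against the pressure-limiting valve, so a manual inflation at emergence could resemble it.

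The protocol places this care at the discretion of a team in which one member knows the allocation, and says that it is not part of the study. Arm-dependent care could then create a T6 difference, or hide one if controls were in effect recruited at emergence. A later analysis plan cannot repair this, because it cannot recover co-interventions that nobody recorded.

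**Working it through.** The protocol gives no figure on this point, so the main check sets its sections side by side.

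**1. Is later care inside or outside the study?** Maintenance of anesthesia says outside. The post-manipulation ventilation, reversal and follow-up sections specify parts of it. The two positions conflict.

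**2. What lies between the manoeuvre and T6?** T5 is 3 minutes after the manoeuvre in the RM group, and before reversal and extubation in both groups. T6 is in PACU. Emergence and extubation therefore fall wholly between T5 and T6. FiO2 is set at 0.4 for maintenance and for the manoeuvre; no value is given for emergence.

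**3. What would the forms show?**

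| Item between T5 and T6 | Recorded? |
|---|---|
| Fluids, blood, vasoconstrictors | Yes (Appendix 3) |
| Desaturation, hypercapnia, laryngospasm, bronchospasm | Yes (Adverse Events) |
| Routine postoperative oxygen | Noted (Follow up measurements) |
| FiO2 at T6 | Implied by the PO2/FiO2 entry (Appendix 6) |
| FiO2 from T5 to extubation | No field |
| Manual inflation, CPAP or further RM | No field |
| Suction | No field |
| Time from T5 to extubation | No field |

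The ventilation form (Appendix 4) ends at T5.

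**4. Who is masked?** The anaesthetists are the PI and the Second Investigator, and the PI is un-blind. At least one care-giver knows the arm, so the masking label is incorrect. The Second Investigator is the intended recorder after the manoeuvre: "The same person will also perform blood gas analyses on the specified time points and postoperative records in PACU". That concerns who reads the outcome, not who treats the child.

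**5. Is the primary endpoint exposed?** No. Compliance is last read at T5, before reversal and extubation, under specified ventilation.

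**6. Illustration of size.** Inputs: 15 per arm (Randomization) and two-sided alpha 0.05 (Sample size determination). The shift d, in SD units, is assumed, because the protocol gives no SD for PO2 or PO2/FiO2. With no true effect, the chance of p < 0.05 is P(|T| > 2.048), where T is noncentral t with 2 × 15 − 2 = 28 df and noncentrality d × √(15/2).

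| d | Noncentrality | Chance of p < 0.05, 15 per arm | Same, 13 per arm |
|---|---|---|---|
| 0 | 0 | 5.0% | 5.0% |
| 0.2 | 0.548 | 8.3% | 7.8% |
| 0.3 | 0.822 | 12.5% | 11.4% |
| 0.5 | 1.369 | 26.2% | 23.2% |

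To give d a meaning: a 1-SD change in 3 of the 15 children in one arm shifts that arm's mean by 3/15 = 0.2 SD; in 8 of 15, by 8/15 = 0.53 SD. The column for 13 per arm uses the protocol's minimum evaluable number (24 df, critical value 2.064).

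**The case against.** The best defence is that the discretion sentence closes a section on management before the manipulation, and that a separate post-manipulation section governs what follows. Control care is defined as no recruitment with moderate PEEP, and ventilation in controls is held unchanged after deflation. A recruiting inflation in a control child would thus depart from the arm definition. The same anaesthetists treat both arms, and discretion alone does not make care depend on the arm. Only secondary outcomes are exposed. The protocol itself says that better oxygenation may not matter clinically in these children, and its Abstract expects no significant blood gas differences.

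Much of this stands, and it limits the point. A reader might infer that all care after maintenance is uncontrolled and invisible; the specified ventilation, reversal agent and noted oxygen rule that out. A reader might also infer that controls are likely to be recruited at emergence. Nothing in the protocol suggests that they will be; it shows only that a departure would leave no trace on the forms.

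The defence does not close the gap. Even if the discretion sentence is read narrowly, extubation still follows undetailed local practice, the emergence items still have no field, and the un-blind PI is still one of the anaesthetists. The oxygenation hypothesis is also stated in Study Objectives, so T6 is not incidental.

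**Conclusion.** The point holds in a limited form. The protocol contradicts itself on whether later care belongs to the study. It claims a masked care-giver that its own staffing does not provide. It also leaves emergence co-interventions from T5 to extubation unrecorded although a secondary efficacy outcome is measured after them. Performance bias at T6 is possible and could not be detected from the forms. The primary comparison of compliance is not affected.

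The 8% to 26% range is not an estimate of bias in this trial. It rests on assumed shifts of 0.2 to 0.5 SD, and the protocol gives neither an SD for PO2 nor any rate of such care. It shows only that, with 15 per arm, modest arm-dependent care would be enough to make a nominally significant T6 result hard to attribute to the manoeuvre. The change is worth making because it is cheap and cannot be made after data collection.

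**What to change.** 1. Reconcile the last sentence of Maintenance of anesthesia with the post-manipulation ventilation, reversal and follow-up sections. State that care from T5 (after the manoeuvre) to T6 follows the same clinician-defined practice regardless of arm. The interval should start at T5, since one starting at deflation would include the manoeuvre itself. The content of that practice is for the clinicians.
2. Add fields to Appendix 4 or 6 for FiO2 from T5 to extubation; any manual inflation, CPAP or further RM; suction; and time from T5 to extubation.
3. Tabulate these by arm beside the T6 results. If they differ between arms, interpret the T6 comparison descriptively.
4. Delete the care-giver from the masked parties in Brief description.

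The cost is some protocol wording, a few extra fields per child and a less favourable masking label. Sample size and the primary analysis do not change.

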### Ventilation Strategy

#### Baseline Ventilation Strategy

Pulmonary ventilation in all patients will be supported with Dräger Primus Anesthesia workstation (SW 4.5n) Ventilator.

Baseline ventilatory parameters include Pressure-Controlled Ventilation (PCV), Positive End-Expiratory Pressure (PEEP) of 5 cm H2O, and Peak Inspiratory Pressure (PIP) of 10-15 cm H2O. These parameters will be titrated to achieve a Vt of 6-7 mL/kg Ideal Body Weight (IBW) and a Respiratory Rate (RR) of 12-20 breaths/min and then finally adjusted to achieve an End-tidal CO2 (EtCO2) of 35-40 mmHg and a target SPO2 of ≥ 97 %.

Ventilatory parameters will be manually recorded from the Anesthesia workstation monitor screen.

[figure not shown]
Ventilatory adjustments will be performed during each period, increasing PIP by 2 cm H2O until a VT of 6-7 mL/kg IBW or within 10% of baseline Vt will be obtained, with a maximum PIP of 25 cm H2O and EtCO2 of 35-40 mmHg. Respiratory rate will be increased by 2 breaths/min after adjusting Vt to maintain an EtCO2 of 35-40 mmHg. Operating room table angle will be measured with a Johnson Magnetic Angle Locator.

#### Recruitment Maneuver (Time and Method of RM)

After deflation of pneumoperitoneum, patients in Control group will continue to be ventilated with the same ventilation settings while RM will be performed to patients in RM group.

Since the locally available Anesthesia Workstation does not permit CPAP > 20 cm H2O, RM will be performed by setting Manual / Spontaneous Ventilation Mode and by setting Adjustable Pressure Limitation (APL) Valve to 30 cm H2O for 30 seconds (Fresh Gas Flow: 5 lt/min, FiO2 0,4), measured by operating room digital clock, while monitoring the patient for signs of adverse effects, such as hemodynamic instability.

## Ventilation Management Flowchart

## Anesthetic Management (post-manipulation)

### Ventilation Strategy (post-manipulation)

The patients of the RM group, after the RM, will be ventilated with the Standardized Ventilation strategy described above. The patients of the Control group will be ventilated with the same strategy throughout the surgical procedure.

### Reversal of the residual blockade, Extubation and Post-Anesthesia Care

At the end of the procedure, residual neuromuscular blockade will be reversed with adequate doses of suggamadex. Tracheal extubation will be performed and the patient will be transported to the Post-Anesthesia Care Unit (PACU) according to the local practice. Patients will be discharged according to standard PACU discharge criteria.

## Measurements

### Primary endpoint

The improvement of  $Com_{dyn}$  will be the primary endpoint of the study.  $Com_{dyn}$  will be measured automatically by the Dräger Primus Anesthesia workstation (SW 4.5n).  $Com_{dyn}$  is determined from  $P_{plateau}$  and Expiratory Tidal Volume and is equal to the measured Total Compliance [ $V_t / (P_{plateau} - PEEP)$ ] minus the System and Hose Compliance determined in the Self-Test of the workstation. Weight-corrected  $Com_{dyn}$  will be calculated by dividing  $Com_{dyn}$  by the weight of patient in kilograms ( $Com_{dyn-wc} = Com_{dyn} / \text{weight}$ ). Time points of measurements are defined below.

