### Materials and Methods

Children undergoing Abdominal Laparoscopy will prospectively be assigned to one of two groups. During the operation, patients in both groups, will be ventilated with Pressure-Controlled Ventilation (PCV) with Positive End-Expiratory Pressure (PEEP) 5 cm H2O and titration to achieve Tidal Volume (Vt) 6-7 ml/kg and End-tidal CO2 (EtCO2) 35-40 mmHg. In the RM group, 3 minutes after deflation of pneumoperitoneum, the investigators will apply RM as a Sustained Inflation with CPAP 30 cm H2O for 30 seconds, by setting Manual / Spontaneous Ventilation Mode and the Adjustable Pressure Limitation (APL) Valve to 30 cm H2O. In both groups, lung compliance will be measured (dynamic compliance) as  $dv/dp$  (ml/cm H2O). Measurements (including hemodynamics and blood gas) will be assessed after a stabilization period of Mechanical Ventilation (MV), as baseline before surgical incision, during the pneumoperitoneum, after deflation, after RM and in Post-Anesthesia Care Unit (PACU). A power analysis will be conducted in order to compare Dynamic Lung Compliance ( $dv/dp$ ) between the two study groups. The improvement in Dynamic Compliance will be the Primary Endpoint of the study. Children will be assigned in a 1:1 ratio to one of the two groups using software-generated blocks.

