## Statistical Methods

### Sample size determination

Power Analysis will be conducted for determination of the Sample Size of this study, in order to estimate a Sample Size that is required so that the study would have adequate power to detect clinically meaningful differences between the two groups, especially concerning Lung Compliance (which is the primary outcome of the study).

For this analysis, we used G\*Power Software (version 3.1.9.2), which is freely available at <http://www.gpower.hhu.de/en.html> from the Heinrich-Heine-Universität of Dusseldorf.

Our Power Analysis is based on a published study in literature, from Manner et al. Assuming that Clinically meaningful difference between the two groups is 20% of the mean value and SD of the observed Lung Compliance is 15% of the mean value, therefore Size effect = 0.2 /

0.15 = 1.33, with two-sided testing, with alpha = 0.05 and power = 0.9 (therefore,  $b = 1 - \text{power} = 0.1$ ). Under these assumptions, G\*Power calculated that we will need minimum 13 patients in each group (totally, 26 subjects) for this study to have adequate power.

Assuming a 15% drop-out rate of the initial number of subjects enrolled to this trial, total number of **30** patients will have to be randomized

Alternatively, using the adequate mathematic formula (see Appendix 2) and the results from the Manner et al study, we confirm a minimum Sample Size of 26 patients.

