### Limitations of the study

This study is aimed to demonstrate a restoration in  $Com_{dyn}$  and gas exchange by the RM. It will not be powered to describe overall pulmonary outcomes, such as postoperative atelectasis or lung infection.

Lung mechanics include a variety of properties approaching lung function in a spherical way; this study, however, is limited to  $Com_{dyn}$  – as an easily accessible parameter in everyday clinical practice.

Our study population will be healthy and heterogeneous in terms of age and therefore size. Although  $Com_{dyn}$  will be adjusted by weight,  $Com_{dyn}$  may be affected by other factors related to age, such as compliance of the chest wall and resistance of the airways. In addition, both the ventilator used and the measurement technique used to obtain  $Com_{dyn}$  could also affect our results.

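### The protocol does not fix whether its primary variable is raw or weight-corrected dynamic compliance, and the stated 90% power is plausible only for the weight-corrected one

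*Protocol*

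**What the plan says.** The protocol describes its compliance outcome in several places, and they do not agree.

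- **Abstract and Primary endpoint section.** Improvement in Com_dyn "will be the primary endpoint of the study". The weight-corrected value is a further quantity that "will be calculated by dividing" Com_dyn by body weight in kilograms; it is never called primary. The Abstract's Materials and Methods gives the unit as ml/cm H2O and says "A power analysis will be conducted in order to compare Dynamic Lung Compliance" between the two groups.
- **Efficacy and Safety Issues.** After stating the expected advantage over control, it says "we consider clinically significant a 20% increase in the weight corrected mean" Com_dyn of the RM group. Later in the same section it calls a 20% rise in plain Com_dyn over baseline, within the RM arm, clinically significant as well.
- **Sample size determination.** The planning assumptions are that the "Clinically meaningful difference between the two groups is 20% of the mean value" and that the "SD of the observed Lung Compliance is 15% of the mean value". Neither is said to be raw or per kilogram.
- **Statistical Analysis.** The main method is a mixed ANOVA between and within groups, supplemented by two-sample t-tests at each time point. The section does not say which compliance variable is analysed.
- **Limitations of the study.** "Our study population will be healthy and heterogeneous in terms of age and therefore size". The next sentence says that Com_dyn will be adjusted by weight.
- **Appendix 4.** Both variables are recorded, at T1 to T5.

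**The concern.** Raw compliance grows with body size. Tidal volume is set per kilogram of ideal body weight (Baseline Ventilation Strategy) and baseline peak pressure is kept within a narrow range. The ratio of volume to driving pressure is therefore roughly proportional to weight. In children from 1 to 14 years, most of the between-child spread in raw Com_dyn will be spread in size.

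The choice of scale thus decides whether the planning SD is reasonable. If the variable named in the endpoint section is compared between groups as it stands, the SD is likely to be well above 15% of the mean, and chance differences in size between two groups of 15 become a serious source of error. If the per-kilogram value is compared, the planning figures can stand. The protocol supports both readings. It also states a clinical threshold on each scale, one of them within a single arm.

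**Working it through.** **1. Reproduce the stated sample size.** Inputs from Sample size determination: difference 20% of the mean, SD 15% of the mean, two-sided alpha 0.05, power 0.90.

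Effect size d = 0.20/0.15 = 1.33. A two-sample t-test (noncentral t) gives power 0.903 with 13 per group and 0.877 with 12. The stated 13 per group is correct for these inputs. The arithmetic is not at issue; the scale of the SD is.

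**2. How uniform must weights be for a raw SD of 15%?** Suppose raw Com_dyn varied only through weight, with weights spread evenly between a lightest and a heaviest child whose weights have ratio r. Then

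CV = (r − 1) / [√3 (r + 1)].

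Setting CV = 0.15 gives r = (1 + 0.26)/(1 − 0.26) ≈ 1.7. With no other variation at all, the heaviest child could weigh at most about 1.7 times the lightest. That is not plausible over ages 1 to 14.

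**3. Power for raw group means at one time point.** The protocol gives no weights, so the weight CV is an assumption and is shown as a range. Take raw Com_dyn = weight × per-kilogram Com_dyn, the two independent, with a per-kilogram CV of 15%:

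raw CV = √[(1 + CVw²)(1 + 0.15²) − 1], d = 0.20 / raw CV, 13 per group.

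| Assumed weight CV | Raw CV | d | Power |
|---|---|---|---|
| 20% | 25% | 0.79 | 0.49 |
| 35% | 38% | 0.52 | 0.25 |
| 40% | 43% | 0.46 | 0.21 |
| 50% | 53% | 0.38 | 0.15 |

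For orientation, weights spread evenly over 10–30 kg have a CV of 29%, and over 10–50 kg a CV of 38%. At weight CV 35–40%, the standard error of the difference in mean weight between two groups of 15 is 0.35 × √(2/15) to 0.40 × √(2/15), or 13–15% of the mean, against a target effect of 20%.

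**4. The within-child comparison.** Simulation used 13 per arm, weights uniform on 10–30 or 10–50 kg, per-kilogram log-SD 0.15, a 20% rise at T5 in the RM arm only, and assumed within-child noise of 3–10%.

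| Comparison between groups | Power |
|---|---|
| Raw Com_dyn at T5 | 0.17–0.26 |
| Raw change, T4c to T5 | 0.83–1.00 |
| Per-kilogram Com_dyn at T5 alone | 0.69–0.83 |
| Log ratio T5/T4c | 0.88–1.00 |

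The third row lies below 0.90 because measurement noise is added to the 15% and a proportional effect widens the RM arm's spread. Using the T4c value recovers most or all of that loss when noise is in this range.

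**The case against.** The best defence is that the per-kilogram value was meant all along. It is defined inside the Primary endpoint section. No compliance variable appears under Secondary measurements. The first 20% threshold is on the weight-corrected mean, and the Limitations say that Com_dyn will be adjusted by weight. On that reading Com_dyn is a generic name, and the planning figures hold together. This stands as a likely intention, but a clause in the limitations does not define a primary variable, and the endpoint text and the Abstract's unit point the other way.

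The second defence is that the main method is a mixed ANOVA. Its group-by-time term compares change within children, so stable body size largely drops out. This also stands, as step 4 shows. But the Statistical Analysis section does not name that term as the primary test, and the sample size was calculated for a difference between two group means.

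Three stronger readings are tempting and not supported:

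- **That raw values cannot have an SD of 15%.** No weights are given, and the scale of the 15% is unstated. Implausible is as far as the text allows.
- **That the trial as a whole is underpowered.** The low figures apply to a raw comparison of means at one time point, including the supplementary t-tests. They do not describe a per-kilogram analysis or the group-by-time term.
- **That success could be declared on a 20% rise within the RM arm alone.** The within-arm figure is an added remark on clinical relevance. The sample size section defines the meaningful difference as between groups, and no success rule rests on one arm.

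Weight is recorded in grams in Table 1 and Appendix 3 but used in kilograms in the endpoint formula. That is clerical.

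**Conclusion.** The conflict is in the protocol's own text and goes beyond detail that could be left to an analysis plan: the named endpoint, the clinical threshold and the planning SD are not tied to one variable. The sample size arithmetic is right, and 90% power is plausible for weight-corrected Com_dyn if the 15% SD is per kilogram. For raw Com_dyn compared between groups at a single time point, power with 13 per group would be about 49% at a weight CV of 20%, falling to 15% at 50%. Those figures rest on assumed weights, a per-kilogram SD of 15% and compliance proportional to weight. The point should be settled before any data are analysed, since two candidate primary variables are recorded for every child.

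**What to change.** - In the Abstract and the Primary endpoint section, name one primary variable: weight-corrected Com_dyn at T5, compared between groups and adjusted for the T4c value. A log scale is a reasonable option, because it gives the result as a percentage ratio, but it is not required.
- In Sample size determination, state that the 20% and the 15% are on the weight-corrected scale.
- In Efficacy and Safety Issues, apply the 20% threshold to the between-group contrast only. Report raw Com_dyn and within-arm change as descriptive.
- As a clerical matter, use one unit for weight throughout.

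The cost is wording and a small change to the analysis. Com_dyn, its weight-corrected value and the T4c measurement are already collected (Appendix 4), and the sample size need not change on this account.
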